6.3.8 Estimated time needed to select this number (i.e. enrolment period)

It is expected that about 24 months of enrolment will lead to about 110 patients enrolled.

6.4 Procedures

6.4.1 Study-related procedures

No study-specific procedures are defined in this protocol and will be performed during this observational study but routine clinical care procedures according to applicable medical guidelines, IFU of the devices used and local policy.

"**Enrolment**" in this observational study means the patient is giving informed consent for use of personal medical data, i.e. the legal prerequisite for being part of this clinical observation. Thus, "**date of enrolment**" is the date of the signature on informed consent. In this purely observational study consent for use of data might be given after index treatment because this treatment is performed in routine clinical care without any studyspecific requirements or definitions and might be performed in an acute setting.

"**Baseline visit**" in this observational study is not a specific personal visit of the patient at the study site but a basket to document all relevant data known at baseline. Thus, medical data reported at baseline visit might represent patient's status even before enrolment, e.g. data on medical history. Use of these data is covered by the informed consent given by the patient.

Due to the acute defects in focus and the corresponding indication of invasive treatment in this purely observational study, "date of enrolment" (=date of informed consent for use of personal medical data) might therefore be after "date of index treatment".

"Start of observation" with respect to the objectives and endpoints of this study is the time point of the index treatment.

6.4.2 Pre-Screening/check of eligibility

Routine clinical care patients are pre-selected and diagnosed for potential eligibility of study participation based on existing data generated in routine clinical care which is not part of this observational study. However, all potentially eligible patients irrespective of their subsequent enrolment into this study will be documented in a screening log within the time period while the study site is open for recruitment to control for selection bias (refer to 6.1.2).

6.4.3 Screening and baseline/enrolment visit (day 1 of observation)

Patients will be screened and enrolled by contracted study sites only, i.e. expert centres. Screening of potentially eligible patients will be performed within routine clinical care. Check for eligibility according to in- and exclusion criteria will be performed using routine clinical care data.

Potentially eligible patients will be informed about the use of their medical data in the study. The patient will be given sufficient time to consider the implications of data use before deciding whether to consent. Participation in this study means following clinical routine care procedures, but allowing for documentation of medical data in a central web-based data base (e-CRF). If the patient is willing to agree, the informed consent form for data use will be provided for signature. As soon as signed informed consent is available, the patient has been enrolled into the study.

Informed consent for use of personal medical data will often be given after the date of index treatment because the treatment is performed in routine clinical care. The fact of enrolment and the enrolment date will in any way be documented within the baseline visit. After signing the consent, patients are checked for eligibility according to in- and exclusion criteria by the participating sites consecutively to minimise selection bias. Study relevant data will be reported in the e-CRF. The e-CRF system will automatically display the patient ID as consecutive number across all participating study sites, i.e. without reference to the recruiting site.

The following data items will be documented of each participating patient at enrolment:

- Demographic data
- Patient's physical status
- Medical history
- Relevant concomitant medication and diseases

Data on the entire clinical stay for treatment of the index defect will be documented.

6.4.4 Treatment of the index defect

The decision of treatment of the index defect lies with the treating physician in routine clinical care. Indication as well as initiation of treatment should follow applicable medical guidelines, local clinical care policy and the IFUs of the devices used.

Initiation of treatment might start as routine clinical care procedure before enrolment into the study (i.e. informed consent of the patient) but data can be entered into the e-CRF after signed informed consent is available (i.e. after enrolment), only.

- Primary EV therapy is defined as the utilisation of EVT as first-line therapy for perforation or leak.
- **Rescue EV therapy** is defined as EVT placement following failure of definitive surgical repair for a perforation or leak.
- **Defect closure following EVT placement** is defined as 1) no evidence of continued leak under direct endoscopic visualization and 2) a negative oesophagram following discontinuation of EVT therapy.

Data regarding index defect, related therapy and outcome following EVT placement will be documented in the e-CRF at the Index-treatment visit.

The following data items will be documented of each participating patient at the index-treatment visit:

- Data of index treatment and related therapy (defect size, type and location of perforation, pre-existing pathology, ASA-classification, Perforation Severity Score (PSS), primary or rescue EVT application, type of endo-sponge placement, type of surgical repair, time to placement of EVT following diagnosis, number of EVT changes, number of days between EVT changes, total length of EVT therapy, relevant laboratory parameters)
- Outcome of index treatment (including 30-day mortality, closure interventions following treatment of index defect, hospital length of stay (LOS), ICU LOS, EVT therapy-specific findings (e.g. migration, dislodgement, erosion), time to oral diet initiation / endoscopic release for stoma relocation following successful defect closure).

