The study protocol does not define specific study procedures for patients enrolled. Therapies and procedures during the course of this study will be performed according to the decision of the treating physician based on current applicable medical guidelines and on local policy in clinical routine care. This includes the prescription and the use of the device of interest and possible measures at enrolment and in follow-up. All devices will be used according to the corresponding IFU, only. The only study-specific obligation within this observational study is to document pre-defined medical and procedural data if available in routine clinical care in the electronic CRF (eCRF) at a level of data quality following international standards on clinical studies.

Flowchart

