6.3 Subjects

About 110 adult female and male patients with acute defects, injuries and wounds in the oesophagus or rectum and an indication of treatment with Suprasorb[®] CNP endo system according to IFU and medical guidelines will be enrolled. Patients' written informed consent to use their routine clinical data according to data privacy standards must be obtained prior to documentation of patients' data in the e-CRF. All patients in whom the device has been used will be followed during routine clinical practice and will visit a site only in the course of their routine clinical care. No additional treatment or medical examinations will be performed.

It will be assured by means of the e-CRF system that treatments of upper GI tract and lower GI tract will be about equally balanced over the total study population.

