6.3.1 Inclusion criteria

- **I1.** \geq 18 years of age
- **12.** Acute transmural defects, injuries and wounds in oesophagus or rectum, including perforations (iatrogenic or spontaneous) and anastomotic insufficiencies (Index defect)
- 13. Indication of treatment with Suprasorb[®] CNP endo system according to IFU and medical guidelines
- I4. Signed informed consent for usage of data

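### The closure definition rests on an oesophageal test for rectal defects too, and the data item matching the primary endpoint is tied to that closure although the endpoint itself is not

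*Protocol*

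**What the plan says.** Section 6.4.4 of the protocol defines defect closure after EVT by two elements that must both be met: an endoscopy that shows no continuing leak, and "a negative oesophagram following discontinuation of EVT therapy". It does not restrict the second element to the upper GI tract and offers no alternative for the rectum.

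The study enrols both sites. The inclusion criterion in 6.3.1 reads "Acute transmural defects, injuries and wounds in oesophagus or rectum", and 6.3 says that the e-CRF will ensure that "treatments of upper GI tract and lower GI tract will be about equally balanced over the total study population".

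Section 6.4.4 then lists what is captured, introduced by "The following data items will be documented of each participating patient at the index-treatment visit". Among the outcomes of index treatment is "time to oral diet initiation / endoscopic release for stoma relocation following successful defect closure".

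Sections 5.2.1 and 6.1.3.1 define healing and the primary endpoint without mentioning closure. The endpoint is the number of days from first use of the device to release for eating (upper GI, and lower GI without a stoma) or to endoscopic release for stoma relocation (lower GI with a stoma).

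**The concern.** There are two linked problems.

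First, the closure definition does not fit the lower-GI half of the population. A rectal patient would not be expected to have an oesophagram in routine care, and a negative one would say nothing about the rectal defect. The protocol separates upper and lower GI when it defines healing and the endpoint, but not when it defines closure.

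Second, the data item that should supply the primary endpoint refers to that closure. A site that follows the item as written could record something other than the endpoint in 6.1.3.1. About 10 sites take part and section 6.5 plans no routine onsite monitoring, so different local readings may go unnoticed. The primary variable could then mean different things at different sites. A statistical analysis plan cannot repair this afterwards if the release date itself was not captured on one common rule.

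**Working it through.** The protocol states no figure on this point, so the check sets the sections side by side. The only arithmetic is the size of the group concerned.

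**1. Endpoint against data item**

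| | Starts at | Ends at | Closure condition |
|---|---|---|---|
| Healing and time to healing (5.2.1) | index use | release | none |
| Primary endpoint (6.1.3.1) | index use | release | none |
| Outcome item (6.4.4) | not stated, or closure | oral diet or stoma release | worded as following successful closure |

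**2. The two literal readings of the item**

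- *As a condition.* Only patients with defined closure have an entry. Patients without it have no value, although 6.1.3.1 gives them an endpoint as soon as they are released.
- *As a time origin.* The item is (release date − closure date). The endpoint is (release date − index date). The difference is (closure date − index date), so every patient whose closure comes after index use gets a time that is too short by that interval.

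The effect on the one-sample log-rank test in section 7 depends on the reading. A later time origin shortens the recorded times and so favours the device. Under the condition reading the direction depends on handling. Leaving patients without closure out of the analysis would favour the device. Counting released patients as unreleased would lower the observed number of events and work against it. The protocol does not show which of these would occur, so only the directions can be given.

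**3. Is the release date listed anywhere else?**

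In the visit table, outcome of index treatment is ticked only under the index-treatment visit. The follow-up items in 6.4.5 are patient status, medication and other treatment, and safety events. No other listed item names the release date.

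**4. Size of the group that the closure definition does not fit**

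Inputs: 110 enrolled, from 99 analysable with a 10% allowance (6.3.7; 99 / 0.90 = 110), and a lower-GI share of about one half (6.3).

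- Enrolled: 110 × 0.5 = 55.
- Analysable: 99 × 0.5 = 49.5, so 49 to 50.
- If the share ran from 40% to 60% (an assumed range): 110 × 0.4 = 44 to 110 × 0.6 = 66.

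These numbers count lower-GI patients. They do not count missing endpoint values.

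**5. Upper-GI patients**

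Section 6.1.1 says "The study protocol does not define specific study procedures for patients enrolled", and data are recorded only if available in routine care. An oesophageal patient with a leak-free endoscopy but no oesophagram would therefore not meet the two-part definition, because a test was not done and not because a leak persisted. The protocol gives no basis for counting such patients.

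**The case against.** The strongest reply is that the endpoint is sound and the closure wording is peripheral. Sections 5.2.1 and 6.1.3.1 never mention closure or an oesophagram, and no closure rate appears among the endpoints or in section 7. The e-CRF is not part of the document. The list in 6.4.4 is a bracketed set of topics opened by the word including, with no entry gate or skip rule. The closing phrase may only describe the usual clinical order. The item also names stoma release explicitly, so lower-GI release was clearly meant to be captured. Finally, a definition that mentions a test does not oblige anyone to perform it.

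Most of this stands, and it rules out three stronger conclusions that a reader might draw:

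- *That the primary endpoint is blocked or the release date cannot be recorded in rectal patients.* No gate is stated and the form is not shown.
- *That about 55 patients lose their endpoint.* That number is only the lower-GI share of enrolment.
- *That a closure rate of 0% would be reported for the lower GI tract.* The protocol plans no such analysis.

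The reply does not remove the mismatch. The closure definition still has no meaning for a rectal defect. The only listed item for the primary endpoint still carries a phrase that the endpoint does not contain, and on either literal reading it departs from 6.1.3.1. The reading as mere clinical order is possible, but the protocol does not say so.

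**Conclusion.** The point holds as a mismatch in definition and data capture, and it should be corrected because it touches the primary variable. The closure definition in 6.4.4 is specific to the oesophagus in its second element and is applied without restriction to a population that is about half rectal (roughly 55 of 110; 44 to 66 if the share is 40% to 60%). The matching outcome item is worded around that closure, while the endpoint runs from index use to release without it.

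Two inferences support this. The definition is taken to apply to all patients because no restriction is given and the items are collected for each participant. The listed items are taken as the protocol's account of what is captured. A loss or distortion of endpoint data is not shown, and no sample size, power or alpha figure changes.

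**What to change.** Reconcile 6.4.4 with 5.2.1 and 6.1.3.1:

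- Delete the closing phrase on successful closure from the outcome item. Record the release date for every patient, whether or not closure is documented, and count the time from index use.
- State that the oesophagram element of the closure definition applies to oesophageal defects only.
- Have the sponsor supply a closure definition for lower-GI defects. Its content is a clinical matter for the sponsor to decide.
- Check that the live e-CRF item matches the corrected wording.

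The cost is the wording of one definition and one e-CRF item, sent to the ethics committees as an amendment under section 9. No new procedure is needed.

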5.2.1 Primary objective

To assess in a routine clinical care setting the performance of Suprasorb[®] CNP endo regarding wound healing in patients with oesophagus and rectum defects of different aetiologies.

Wound healing is defined as release for oral food intake (in upper GI tract use) or endoscopic release for stoma relocation (in lower GI tract use).

Time to wound healing is consequently defined as time from index use of Suprasorb[®] CNP endo to date of release for oral food intake (in upper GI tract use) or endoscopic release for stoma relocation (in lower GI tract use).

5.2.2 Secondary objectives

To assess in a routine clinical care setting in this patient population

- 1. adequate safety of the use of Suprasorb[®] CNP endo, and
- 2. duration of hospital care with use of Suprasorb[®] CNP endo.

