6.1.3 Endpoints of the study

6.1.3.1 Primary endpoint

Time period in days from index use of Suprasorb[®] CNP endo to release for oral food intake (in upper GI tract use) or endoscopic release for stoma relocation (in lower GI tract use).

In case of lower GI tract use and no stoma present, time period to release for oral food intake is the relevant endpoint.

6.1.3.2 Secondary endpoints

- 1. Number of SAEs related to defect treatment within total observation period.
- 2. Number of nights in hospital for therapy of index defect.
- 3. Number of nights at the ICU during hospital stay for therapy of index defect.

Nights at an intermediate care unit (IMC) will not count for this secondary endpoint.

SAEs will be adjudicated by an independent Clinical Event Committee (CEC) according to standard definitions. Wherever reasonable, endpoints will be normalised to one year of follow-up to adapt results to varying follow-up periods.

"Index defect" describes for each study patient the defect(s) which lead to the clinical indication of treatment with Suprasorb[®] CNP endo system according to IFU and medical guidelines as defined in 6.3.1.

"Index therapy" describes for each study patient the first use of Suprasorb[®] CNP endo for therapy of the index defect.

6.1.4 Methods and timing for assessing, recording, and analysing variables

Only data which can be obtained from routine clinical care files of the patients will be recorded. Data of routine clinical care visit after study enrolment will be reported in the e-CRF. Data will be derived from clinical records and findings, radiological assessments, observations or other sources (e.g. hospital records, clinical and office charts, electronic patient records, laboratory notes).

Within this observational study timing of measures and clinical data to be reported are determined by routine clinical care in line with applicable medical guidelines and local policies. The study protocol just defines some procedural recommendations.

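### The listed e-CRF outcome item does not match the primary endpoint: it appears to start at defect closure rather than index use, and for oral intake it names a different event

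*Protocol*

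**What the plan says.** The endpoint is defined consistently. Protocol 6.1.3.1 gives it as "Time period in days from index use of Suprasorb[®] CNP endo to release for oral food intake (in upper GI tract use"), with endoscopic release for stoma relocation as the lower GI event. It adds: "In case of lower GI tract use and no stoma present, time period to release for oral food intake is the relevant endpoint". Section 5.2.1 agrees on the origin: "Time to wound healing is consequently defined as time from index use of Suprasorb" and so on, up to the date of release. Section 6.4.1 sets the start of observation "with respect to the objectives and endpoints of this study is the time point of the index treatment". Section 7 describes the analysed time as running from index therapy, which 6.1.3 defines as the first use of the device.

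Section 6.4.4 lists what is documented at the index-treatment visit. Among the outcomes is "time to oral diet initiation / endoscopic release for stoma relocation following successful defect closure". The same section defines closure by two conditions, the second being "a negative oesophagram following discontinuation of EVT therapy".

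The baseline items (6.4.3) are demographics, physical status, history, and concomitant medication and diseases. The follow-up items (6.4.5) are patient status, medication and other treatment, and safety events. The visit table assigns the outcome of index treatment to the index-treatment column only.

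**The concern.** The item differs from the endpoint in three respects.

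- **Clock.** The same list contains "time to placement of EVT following diagnosis", where the word after which the interval runs is plainly its start. Read the same way, the outcome item runs from closure. Because closure is confirmed after vacuum therapy stops, the therapy period lies outside the recorded time.
- **Event.** For upper GI patients, and lower GI patients without a stoma, the endpoint is release for oral intake, but the item is initiation of oral diet. A released patient may start eating later or not at all.
- **Who gets a value.** A patient without successful closure has no value, although 6.1.6 sets intention to treat as the analysis principle.

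At stake is the one variable tested as confirmatory. A one-sample log-rank test compares observed events with those expected over each patient's time at risk. Days missing from that time lower the expected count and can push the result towards superiority. Replacing release by initiation would push the other way; the documents give no figure for its size.

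**Working it through.** **Comparison of the texts**

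| | Endpoint (5.2.1, 6.1.3.1, 6.4.1, 7) | Listed item (6.4.4) |
|---|---|---|
| Origin | first use of the device | successful closure, on the natural reading |
| Event, upper GI, and lower GI without stoma | release for oral intake | oral diet initiation |
| Event, lower GI with stoma | endoscopic release for stoma relocation | the same |
| Patients without closure | included | no value |

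The listed items do not allow the index-based time to be rebuilt reliably. Total length of vacuum therapy is listed, but the gap between its end and confirmed closure is not.

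**Size if closure-based times were analysed**

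The point depends on no figure in the plan; this is an illustration. Inputs: 99 analysable patients, 3 months of follow-up, exponential times and a two-sided 4.92% level (6.3.7), so 2.46% in the direction of superiority and a critical value of 1.967. The reference is 56% with the event at 6 months; the plan's derivation reproduces as 50% + 2 × 2.8% = 55.6%. Durations come from 3.2: 12 days (mean therapy, upper GI), 14 days (median therapy, upper GI) and 40.5 days (median healing, colorectal). The 13 expected events stated in 6.3.7 are not used.

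- Reference hazard: λ0 = −ln(0.44)/6 = 0.1368 per month.
- Test: Z = (O − E)/√E, with E = λ0 × total time at risk.
- Correct clock, no device effect: O = E = 99 × (1 − e^(−3 × 0.1368)) = 33.3. In simulation about 3% exceed the critical value, slightly above 2.46% because Z is only approximately normal.

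*Model A: release only after closure, and still 56% at 6 months from index use.* After a therapy period of V months the hazard is λ′ = −ln(0.44)/(6 − V), so the apparent hazard ratio is 6/(6 − V).

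- 12 days: V = 12/30.44 = 0.394; ratio 6/5.606 = 1.07.
- 14 days: V = 0.460; ratio 6/5.540 = 1.08.
- 40.5 days: V = 1.330; ratio 6/4.670 = 1.285 (about 1.29).

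For 12 days with 3 months counted from closure, λ′ = 0.1464, O = 99 × (1 − e^(−3 × 0.1464)) = 35.2 and E = 35.2/1.07 = 32.9.

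Simulated false superiority (40,000 runs):

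| Therapy period | Rate |
|---|---|
| 12 days, all patients | about 7% |
| 14 days in half, 40.5 days in half | about 14% (3 months from index use) to 19% (3 months from closure) |

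On the index clock the same patients, with any one of these durations applied to all, give at most 0.6%.

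*Model B: events may precede closure, and such patients are dropped.* Observed and expected counts fall together, to about 28.1 each (12 days) and about 22.1 each (14/40.5 days). The rates are 3.0% and 3.1%, so there is no inflation.

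**The case against.** The strongest reply is that the analysed time is fixed four times over, always from index use or index therapy, and that nothing says the 6.4.4 item is the analysed variable. That stands. A reader might infer that the plan will analyse times that leave out the vacuum-therapy period; the documents do not support this.

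Second, the outcome list is introduced as non-exhaustive, 6.4.3 says that data on the whole stay are documented, and the e-CRF is not shown. That also stands. One cannot say that this is the only e-CRF item for the endpoint, only that it is the only one the protocol lists. Deriving times from dates is ordinary SAP work, but an SAP cannot supply a date that was not collected.

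Third, the reference to closure may be a condition or a description of sequence; the same list uses the word in that looser way for closure interventions. This is possible. The item would then state no origin and still leave patients without closure unrecorded.

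Fourth, the event is identical for lower GI patients with a stoma, and 6.3 aims for about equal numbers of upper and lower GI treatments. The event mismatch is therefore partial.

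Finally, a reader might subtract the therapy days from each patient's time at risk but keep all 33.3 events, and so arrive at about 19% (12 days) and 63% (14/40.5 days). Those figures do not hold. They count events that precede closure, 5.2 and 11.2 of the 33.3, with no time at risk, although an event following closure cannot come before it.

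**Conclusion.** The inconsistency is real and concerns the primary variable. The listed item conflicts with the endpoint on origin in its natural reading, on event for oral intake, and on coverage of patients without closure. It is a data-capture risk worth correcting, not an error in the planned analysis.

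If closure-based times did reach the analysis, the false superiority rate would lie between no inflation (about 3%) and about 7% for 12 days, or 14 to 19% for 14/40.5 days, against 2.46% nominal. These figures assume a fixed therapy period per site of defect, an exponential reference of 56% at 6 months applied to all patients, and a reference clock that starts with treatment. That reference comes from stoma relocation; the protocol gives no control curve for oral intake. The direction is therefore firmer than the size.

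**What to change.** In 6.4.4, replace the duration item by calendar dates: first use of the device; release for oral food intake (upper GI, and lower GI without stoma); endoscopic release for stoma relocation (lower GI with stoma). Record them for every patient whether or not closure is achieved, and add the release dates to the follow-up items in 6.4.5 and the visit table, so that releases after discharge are captured. State once that the primary time is the release date minus the date of first device use. Keep the dates of closure and of oral diet initiation as descriptive items only.

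The cost is a wording change in the protocol and, if the e-CRF lacks these dates, a few added fields. No procedure is added. Since data are recorded only where routine care provides them, sites should be asked whether the release date is routinely noted.
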